Effective molecular surveillance may be only marginally affected by a test’s lower analytical limits of detection (26). Although molecular tests may show false negatives (FN) early on or late in the infection cycle when viral load is increasing and decreasing, respectively, the viral burden corresponding to a positive screening test is not established (29). Interim results demonstrate that when compared to the diagnostic (laboratory-based qualitative RT-PCR), screening test in controlled settings (in urgent care clinic, hospitalized and nursing home patients) is $\geq 95\%$ sensitive and $\geq 99\%$ specific (30). In our study, the screening test utilizes samples collected: a) at the workplace, b) by the participant, c) using nasal swabs followed by point-of-care testing, d) in a low infrastructure community setting, e) by minimally trained professionals. The screening test was granted emergency use authorization without a detailed study on end-user needs in the real-world, but each of the above variables introduces a potential source of error in results.

PROTOCOL TITLE: Keeping rural minority ‘essential’ workplaces open safely during the COVID-19 pandemic: The role of frequent point-of-care molecular workplace surveillance for miners

Our *objective* is to determine the ability of the screening test to correctly detect the presence of the virus in upper respiratory specimens in the real-world setting. This will be accomplished by evaluating screening test performance at the workplace by quantifying viral loads from self-collected nasal swab and health personnel-collected nasopharyngeal (NP) swab specimens, using quantitative RT-PCR (RT-qPCR). Our *working hypothesis* is that the sensitivity of the screening test in a real-world study setting is a) comparable to that described by others in controlled settings, and b) positively associated with viral load in upper respiratory specimens. Successful completion of this study will help determine the real-world performance of less sensitive screening tests in disease settings of mild severity.

Table 5: Test findings studied in Aim 2

Measurement	Biological specimen	N	Purpose
Screening test (qualitative)	Self-collected nasal swab	less than 250	Workplace surveillance
Diagnostic test RT-PCR (qualitative)	Healthcare personnel collected NP swab	less than 250	Establish sensitivity, specificity & diagnostic accuracy of screening test

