Power calculations: If we recruit less than 250 miners, we have the power to estimate 85% acceptance rate \pm 4.6%. For a comparison of acceptance rates between predictor groups, we assume, for example, non-Hispanic white and minority miners (1/3 and 2/3 of the study population respectively) have 85% and 80% acceptance respectively. We used simulation to assess power for Poisson regression analyses where the rate denominator (offset) is the number of miner workdays, assumed to be 95% of possible days. For these conditions, power is 94% for a 5% lower acceptance rate for minority miners. We also used simulation to assess the planned longitudinal analysis of miner acceptance by assuming that miners attended work 95% of the shifts, that initial acceptance is 85% and that there is a linear decline in acceptance over the study to a final acceptance rate of 80%. For repeated measures on about 200 miners, the power to detect a linear decrease to 80% is 95%.

13.2. Specific Aim 2:

Statistical analysis: We will compare screening test performance measures between our real-world study setting and controlled settings (as published by others). We will use a one-sample Exact test for a binomial proportion to test whether sensitivity for the screening test is the same as that published. We will correlate screening test results with quantitative viral loads, and perform Bland-Altman plots to reveal systematic differences between viral loads collected by the two sampling methods.

Power Calculations: If we conservatively estimate identifying 25 true positive miners, using a one-sample Exact test for a Binomial proportion equal to the comparison test, we have the power (>90%) to detect a difference between the screening and the comparison test if the screening test sensitivity is 90% or lower.

13.3. Specific Aim 3:

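### Aim 2 tests sensitivity against an interim published figure as if it were known exactly, and the stated power above 90% does not hold against the 95% that the protocol cites

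*Combined protocol and SAP*

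**What the plan says.** Hypothesis 2a (Section 1 and Section 3.2) is that the screening test's sensitivity at the mine is comparable to that reported by others in controlled settings. Section 3.2 describes the outside evidence as follows: "Interim results demonstrate that when compared to the diagnostic (laboratory-based qualitative RT-PCR), screening test in controlled settings" is at least 95% sensitive and at least 99% specific. No point estimate, count of positives or confidence interval accompanies the figure.

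The analysis is in Section 13.2: "We will use a one-sample Exact test for a binomial proportion to test whether sensitivity for the screening test is the same as that published". The power paragraph there begins "If we conservatively estimate identifying 25 true positive miners" and claims "the power (>90%) to detect a difference between the screening and the comparison test" "if the screening test sensitivity is 90% or lower". It does not give the null value. Aim 2 has no stated alpha or sidedness; the 0.025 in Section 13.3 belongs to Aim 3.

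The assay is not fixed either. Section 2 asks only for sensitivity of at least 80%, and Section 12.1 leaves the final choice to later advice.

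**The concern.** Hypothesis 2a sets one estimate against another, and both carry sampling error. A one-sample test counts only the error from this study's 25 or so infected miners and takes the published value as a constant. If that value rests on few positives, it may lie well above the true sensitivity, possibly at 100%, where a single missed infection in 25 is enough to reject. The trial could then report that workplace testing performs differently from controlled settings when the two sensitivities are equal.

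This is the only formal test planned for 2a, so nothing else in the plan would correct it. The power claim matters for the same reason: it depends on a null value that is not written down.

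**Working it through.** **Inputs.** From the documents: 25 true positives and a sensitivity of 90% under the alternative (Section 13.2); published sensitivity of at least 95% (Section 3.2). Assumed because not stated: alpha 0.05, two-sided by the minimum-likelihood method; number of published positives n0 from 20 to 500.

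**Step 1: the plan's own power figure.** Let X be the number detected among 25. Against a null of 0.95 the exact test rejects at X ≤ 21, that is, at four or more misses.

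- Size: 1 − (0.0930 + 0.2305 + 0.3650 + 0.2774) = 3.4%, the bracket being P(X = 22), …, P(X = 25) at 0.95.
- Power at 0.90: 1 − (0.2265 + 0.2659 + 0.1994 + 0.0718) = 23.6%. With a doubled-tail p-value it is 9.8%.

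Other nulls:

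| Null | Rejects at | Power at 90% sensitivity |
|---|---|---|
| 0.95 | 4 or more misses | 23.6% |
| 0.97 | 3 or more | 46.3% |
| 0.98 | 3 or more | 46.3% |
| 0.99 | 2 or more | 72.9% |
| 0.998 | 1 or more | 92.8% |

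One miss rejects only if 1 − p0^25 ≤ 0.05, so p0 ≥ 0.95^(1/25) = 0.998. Power is then 1 − 0.9^25 = 92.8%. The stated figure above 90% is reproduced only there. For 90% power at 95% against 90%, about 290 positives would be needed two-sided, or 256 one-sided.

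**Step 2: false-difference rate of the planned test.** Let the published count be K ~ Bin(n0, p) and the study count X ~ Bin(25, p), with the same true p. The rate is the sum over k of P(K = k) × P(the one-sample test with null k/n0 rejects), computed by exact enumeration:

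| n0 | p = 95% | p = 97% | p = 99% |
|---|---|---|---|
| 20 | 29.9% | 30.3% | 18.3% |
| 30 | 20.6% | 22.9% | 16.5% |
| 50 | 9.6% | 13.1% | 13.5% |
| 100 | 5.8% | 7.0% | 9.1% |
| 150 | 5.1% | 5.5% | 6.5% |
| 200 | 3.8% | 3.4% | 4.4% |
| 500 | 3.1% | 3.0% | 3.0% |

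**Step 3: where the excess comes from.** At p = 95% and n0 = 20, the published estimate is 100% with probability 0.95^20 = 35.8%. Any miss then rejects, with probability 1 − 0.95^25 = 72.3%. The product, 25.9 points, makes up most of the 29.9%. Given a published estimate below 100%, the rate is 0–7% over the whole grid.

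**Step 4: null fixed at the stated 95%.** The rejection region is X ≤ 21 whatever the source. The rejection rate is 3.4% at true 95% and 0.01% at true 99%. It exceeds 5% only if 95% overstates the true value: 13.5% at true 92% and 23.6% at true 90%.

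**Step 5: a two-sample comparison.** A Newcombe 95% interval for the difference excluded zero in 0.2–4.6% of cases for p = 93%, 95% and 97% and n0 from 20 to 200. A two-sided Fisher test rejected in at most 2.6% for p from 95% to 99% and n0 from 20 to 500. For 95% published against 90% here, power with the Newcombe interval is about 12% at n0 = 50 and about 25% at n0 = 500.

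**The case against.** The strongest reply is that the size of the problem rests on a denominator that the documents do not give. On their only figure, a null fixed at 95%, the test has size 3.4%, and a source study of 100 to 150 positives would leave an excess of only about one to two points at true sensitivity of 95–97%. The large rates come mainly from a published estimate of 100%, which the documents do not report. The comparator is also open: the assay is undecided, and larger published data may exist by the time of analysis. Aim 2 does not feed the seropositivity outcome that Aim 3 labels primary.

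All of that stands as a limit on size. It does not remove the defect: the plan words 2a as a comparison with published performance, and no text makes any allowance for the error in that figure. An undecided comparator is a reason to fix the method now.

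A reader might infer that the test declares false differences far more often than its nominal level. The documents do not support that: Aim 2 states no level, and the rate may be near 30% or below 5%. A reader might also infer from the power claim that a null of practically 100% was intended, under which equal true sensitivities of 95%, 97% or 99% would be called different in 72%, 53% or 22% of trials (1 − p^25). The null is never stated, and the power figure may simply be wrong.

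**Conclusion.** The point holds in conditional form. The planned test ignores the sampling error of an interim published estimate. With 25 true positives, equal true sensitivity of 95–97% and an assumed two-sided 0.05, the consequence is serious if the published figure rests on a few dozen positives, modest at about 100 and absent by about 200. Inflation cannot be asserted as a fact about this trial, because the published count is missing and a null fixed at 95% gives no inflation when the true value is 95% or higher.

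The power statement is the firmer finding. Under the same assumed alpha, power above 90% does not follow from 25 positives and the protocol's own 95%; it is 23.6%. At that null, failing to detect a real five-point shortfall is much the likelier error. Both matters should be corrected before the Aim 2 analysis.

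**What to change.** In Section 13.2, replace the one-sample test with a comparison of the two sensitivities, using the published numerator and denominator for the assay actually used. Report the difference with a Newcombe 95% interval, or use an unconditional exact test. If only the bound is available, keep the one-sample test but call 95% a fixed performance goal, and do not word Hypothesis 2a as a comparison with the published estimate.

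State the comparator value and its source, alpha and sidedness. Restate the power for 90% sensitivity on the chosen basis: about 24% for the one-sample test against 95%, or about 12–25% for the two-sample comparison with 50 to 500 published positives.

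The cost is a few sentences in the analysis section and a re-run power calculation; no data collection changes. The downside is that the power becomes much less favourable than stated, so 2a is better presented as estimation with an interval than as a well-powered test.

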Quantitative RT-PCR	Self-collected nasal swab	less than 250	Quantitate viral load vis-à-vis screening test
Quantitative RT-PCR	Healthcare personnel collected NP swab	less than 250	Quantitate viral load vis-à-vis screening test
Sputum biomarkers	Spontaneous home sputum samples	Less than 250	Quantitate inflammation

Research design: In this cross-sectional study, sensitivity, specificity and diagnostic accuracy (31) of the screening test on a self-collected nasal swab will be established by comparison with diagnostic test (qualitative RT-PCR), the latter conducted on an NP swab collected on the same day by trained health personnel, in a CLIA certified clinical laboratory (TriCore; Table 5). Also, since the diagnostic test is qualitative, we will also quantify viral load (\log_{10} copies/mL) from repeat nasal (self-collected) and NP (collected by healthcare personnel) swab specimens using RT-qPCR established in the [name] research laboratory (32). Viral load will be determined with primers and probes (N1 and RP) using the CDC 2019-nCoVEUA-01 diagnostic panel (33). Miners with any positive screening test (plus a sample of ~200 miners with a negative test) will undergo the above testing procedures. Database management and timelines will be similar to those described in Aim 1.

3.3. Specific Aim 3:

The role of frequent point-of-care molecular workplace surveillance to monitor and prevent the spread of SARS-CoV-2 is inadequately studied, particularly in rural essential workplaces. Our *objective* is to examine the effectiveness and costs of frequent point-of-care molecular workplace surveillance in rural essential workers. Our *working hypothesis 3A* is that frequent point-of-care molecular testing over up to twelve months in the intervention mine will result in lower incident seropositivity rates compared to the control mine. *Hypothesis 3B* is that frequent point-of-care molecular surveillance in the intervention mine is cost-effective compared to the control mine. The *rationale* for the

PROTOCOL TITLE: Keeping rural minority ‘essential’ workplaces open safely during the COVID-19 pandemic: The role of frequent point-of-care molecular workplace surveillance for miners

proposed work is that by establishing its effectiveness, implementation costs, and cost-effectiveness, our study will increase the real-world utility of workplace molecular testing, resulting in a novel primary prevention strategy targeted at rural essential workers.

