Additional questionnaire: Demographics (age or DOB, gender or sex, race and ethnicity, education, household income, insurance, Mailing residential address and if PO Box, physical mailing address, phone number, medical history, smoking, history of prior COVID hospitalization, Testing and vaccination history	Once between 6 and 12 months, using paper, or electronic (e.g. REDCap)	None

PROTOCOL TITLE: Keeping rural minority ‘essential’ workplaces open safely during the COVID-19 pandemic: The role of frequent point-of-care molecular workplace surveillance for miners

Web-based phone app questionnaire: Symptoms; frequency of cloth face-covering use outside the mine ; vaccination history, infected contacts, & history of prior COVID infection	Each work shift via the phone app	
Measured fever screen	Each work shift measure, recorded via REDCap (normal vs. abnormal)	
Nasal swab (self-collected) screening test	Alternate shift collection plus test acceptance data entered into REDCap	None
Nasopharyngeal swab (trained professional or TP-collected) diagnostic test (RT-PCR, TriCore labs)	All abnormal screening tests (collected at TriCore Cibola) & sample (n=approximately 200) of normal screening tests (collected at mine site) plus test acceptance data entered into REDCap	None prescribed
Nasal (self-collected) and nasopharyngeal swab (TP-collected) research test (RT-qPCR, [name] labs)	All abnormal & sample of normal tests as above	None prescribed
Serology	Blood sample at baseline, 3, 6, and approximately 12 months plus test acceptance data entered into REDCap	
Occupational dust exposure intensity	Every work shift via job-exposure matrix created by occupational safety team via REDCap	
Daily county incidence and prevalence data	Recorded daily by study coordinator from public health records entered into REDCap	
Focus group discussions and/or individual interviews to study “testing hesitancy”	Yes	No
Spontaneous home collected sputum sample	Yes once at approximately 12 months	No

12.1. Specific Aim 1:

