Miners work one of two twelve-hour shifts daily, in repeated patterns of 4 days on followed by 4 days off work. At the beginning of each alternate work shift, each miner, irrespective of symptom status, will provide supervised self-collected midnasal swabs to trained mine safety personnel at the mine entrance. The safety personnel will run the screening test on swabs at the mine site. Miners with a positive screening test will undergo a confirmatory diagnostic test, and will be: 1) referred to their healthcare provider; 2) offered telemedicine evaluation at UNM, for those interested, and 3) removed from the workplace per CDC guidance (28). The final assay for the screening test will be decided based on advice from the NIH RADx-UP Coordinating and Data Collection Center. Acceptance data will be entered at the mine site by the safety personnel into a Research Electronic Data Capture (REDCap) database. Focus group discussions and/or individual interviews will be performed in a sample of subjects at the intervention mine in NM to better understand ‘testing hesitancy’ towards the end of the study.

12.2. Specific Aim 2:

Miners with any positive screening test (plus a sample of ~200 miners with a negative test) will undergo trained professional collected NP swab (for RT-PCR diagnostic testing), self-collected nasal swab (for RT-qPCR) and trained professional collected NP swab (for RT-qPCR). Database management and timelines will be similar to those described in Aim 1.

12.3. Specific Aim 3:

PROTOCOL TITLE: Keeping rural minority ‘essential’ workplaces open safely during the COVID-19 pandemic: The role of frequent point-of-care molecular workplace surveillance for miners

In brief, at the beginning of each work shift, trained mine safety personnel will obtain the following: 1) 24-hour history of SARS-CoV-2 symptoms, provider diagnosis of infection, close contact with any infected, vaccination, and use of cloth face-covering in public settings outside the mine, using a web-based phone app, also available using a computer connected to the Internet; and 2) body temperature measurement using a no-touch forehead infrared thermometer. The web-based phone app, created by Ingenuity Software Inc., will be accessed by the subjects with password protection. The information will be encrypted during data transfer to a secure server that resides at the UNM HSC and will auto-populate the REDCap database. The phone app has been approved by UNM HSC IT.

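### Aim 2: the >90% power claim for screening-test sensitivity fails against a published comparator of 95–99%, and the rule for verifying negative screens leaves open whether sensitivity can be estimated

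*Combined protocol and SAP*

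**What the plan says.** Section 3.2 describes Aim 2 this way: "In this cross-sectional study, sensitivity, specificity and diagnostic accuracy (31) of the screening test on a self-collected nasal swab will be established by comparison". The reference is a qualitative RT-PCR on a same-day nasopharyngeal swab. On who is verified it says: "Miners with any positive screening test (plus a sample of ~200 miners with a negative test) will undergo the above testing procedures". It adds: "Database management and timelines will be similar to those described in Aim 1". Aim 1 runs for up to twelve months with a screen on alternate shifts. Section 12.2 repeats the rule in terms of miners. The overview table in Section 12 counts tests instead: "All abnormal screening tests (collected at TriCore Cibola) & sample (n=approximately 200) of normal screening tests". Table 5 gives fewer than 250 for the RT-PCR comparison. No section says how or when the negatives are chosen, and none mentions weighting.

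Section 13.2 plans a "one-sample Exact test for a binomial proportion to test whether sensitivity for the screening test is the same as that published". Its power paragraph begins "If we conservatively estimate identifying 25 true positive miners" and claims "the power (>90%) to detect a difference between the screening and the comparison test if the screening test sensitivity is 90% or lower". It states neither a numerical null value nor an alpha. Section 3.2 cites interim results from controlled settings of at least 95% sensitivity and at least 99% specificity. Section 2 leaves the product open and asks only for sensitivity and specificity of at least 80%.

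**The concern.** With 25 infections and a true sensitivity of 90%, two or three misses are expected. A comparator of 95% predicts one or two. An exact test cannot separate these with power above 90%, so the stated figure looked wrong whatever the verification scheme.

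Separately, RT-PCR depends on the screening result: every positive is verified but only some negatives. If the verified negatives are a small share of all negatives, missed infections rarely enter the sensitivity denominator. The estimate then reflects the sampling more than the test. Falsely high sensitivity would matter here, because the test is meant to help keep a workplace open safely.

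**Working it through.** **Inputs.** n = 25 and true sensitivity 0.90 (Section 13.2). Null p0 = 0.95 (Section 3.2, lower limit); 0.97, 0.98 and 0.99 are assumptions. Alpha is not stated, so 0.05 is assumed. Steps 1–3 assume every infection is verified.

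**1. Reproducing the plan's figure.** Against a perfect comparator any miss rejects, so power = 1 − 0.9^25 = 92.8%. One miss in 25 rejects at one-sided 0.05 only if 1 − p0^25 ≤ 0.05, that is p0 ≥ 0.95^(1/25) = 0.998. With a doubled tail the condition is p0 ≥ 0.975^(1/25) = 0.999.

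**2. Power against the published comparator.** Let c be the largest x with P(X ≤ x | 25, p0) within alpha. Power is P(X ≤ c | 25, 0.90).

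| p0 | c (tail), one-sided 0.05 or minimum-likelihood two-sided 0.05 | Power | c (tail), doubled-tail two-sided 0.05 | Power |
|---|---|---|---|---|
| 95% | 21 (0.034) | 23.6% | 20 (0.007) | 9.8% |
| 97% | 22 (0.038) | 46.3% | 21 (0.006) | 23.6% |
| 98% | 22 (0.013) | 46.3% | 22 (0.013) | 46.3% |
| 99% | 23 (0.026) | 72.9% | 22 (0.002) | 46.3% |

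If the 25 are screen-positive infections, about 25/0.9 ≈ 28 are infected. Power (one-sided 0.05) is then 30.5% at p0 = 95% and 78.5% at 99%.

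**3. What 25 infections can detect.** At one-sided 0.05, 90% power needs a true sensitivity of about 75% (p0 = 95%), 80% (97–98%) or 85% (99%). To keep 90% power at a true 90%, about 256, 116, 78 or 52 RT-PCR positives are needed for p0 = 95%, 97%, 98% or 99%.

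**4. If positives accumulate.** Section 12.1 describes shifts "in repeated patterns of 4 days on followed by 4 days off work", so alternate-shift testing gives 365/8 × 4/2 ≈ 91 tests per miner-year. Section 7.1 caps the count below 60 and Section 13.1 below 120. As a range, take 200 × 60 × 0.85 = 10,200 tests to 250 × 91 = 22,750. The upper end is generous, since it assumes full acceptance. At 99% specificity nearly all are negative, and the verified fraction f is 200/10,098 = 0.0198 to 200/22,522 = 0.0089.

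Unweighted sensitivity = Se / (Se + (1 − Se) × f):
- Se = 0.80: 0.8/(0.8 + 0.2 × 0.0198) = 99.5%, to 0.8/(0.8 + 0.2 × 0.0089) = 99.8%.
- Se = 0.50: 98.1% to 99.1%.

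With 25 infections at Se = 0.80, five are missed, and 5 × f = 0.10 to 0.04 of them are expected among the 200. Taking detected cases as binomial and sampled misses as hypergeometric, the two-sided exact test rejects in under 0.01% of studies against 95% and in 0.1–0.4% against 99%. Complete verification of the same 25 gives 76.6% and 97.3%. Nor can 25 of 25 reject upward against 95%, since 0.95^25 = 0.28.

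**5. If one round is meant.** With 250 miners and 25 infected, about 200 of 225 negatives are verified (f ≈ 0.89). At Se = 0.80 the unweighted value is 0.8/(0.8 + 0.2 × 0.89) ≈ 82%; at 0.90 it is about 91%. Simulated power at a true 90% is about 17% (p0 = 95%) and 66% (p0 = 99%).

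**The case against.** The figure above 90% is not an arithmetic slip. It reproduces as 92.8% if the comparison test in the power sentence means RT-PCR itself, taken as perfect. That may be its origin, but the analysis sentence in the same section tests against the published sensitivity, so the power does not describe the planned test. It is also fair that alpha is unstated and that values above 95% are not in the document. Even so, no convention tried (one-sided 0.025, 0.05 or 0.10; two-sided 0.05) reaches 90% anywhere from 95% to 99%.

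A reader might infer that the verification scheme certainly makes the sensitivity result uninformative. The text does not support that. Section 3.2 calls the study cross-sectional and counts miners, and 25 + 200 = 225 fits Table 5. The timeline sentence also covers database management and is weak evidence for a year of accumulation. On the other side stand the phrase about any positive screen, the overview table's count of tests and the Aim 1 timeline. The 10% baseline seropositivity in Section 13.3 would be 25 of 250, but seropositivity is not current RT-PCR positivity. Neither reading is settled.

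A reader might also infer that specificity has no planned analysis. Section 13.2 says performance measures will be compared, which can cover specificity, although no test is named. An unweighted specificity would be biased downward only to the extent that verification is unequal.

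**Conclusion.** The power claim is wrong as written. For a comparator of 95–99%, complete verification and alpha 0.05, power at a true sensitivity of 90% is about 24–73%, or about 10–46% with a doubled tail. This needs no assumption about how negatives are sampled; a single round with incomplete verification lowers power slightly further.

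The verification problem is real but conditional. It requires that positives accumulate over up to twelve months and that the negatives are drawn without regard to infection status. Then the unweighted exact test cannot practically contradict Hypothesis 2a against a comparator of 95% or more, even at a true sensitivity of 80%. If a single round is meant, the bias is about two percentage points or less at true sensitivities of 80–90%. What holds on any reading is that the sections disagree on unit and period and give no selection rule.

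The effect is confined to the Aim 2 accuracy results. The Aim 3 seropositivity outcome and the Bland-Altman comparison of viral loads are not touched.

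**What to change.** 1. In Section 13.2, state the null sensitivity (for the product actually chosen), alpha and sidedness. Withdraw the figure above 90% and restate power for that comparator. Alternatively, state the true sensitivity that 25 positives can detect with 90% power: about 75% for a null of 95%, about 85% for 99%, at one-sided 0.05.
2. Reconcile Sections 3.2, 12 and 12.2 and Table 5 on unit (miners or tests), period, and how and when the negatives are selected. If one round is meant, say so.
3. If accumulation is meant, draw the 200 or so at random from negative tests over calendar time and record the total number of negative tests. Use inverse-probability-of-verification (Begg-Greenes) weights, clustered by miner, for the accuracy measures. Report weighted sensitivity descriptively with its interval instead of relying on the unweighted exact test.

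The cost is wording and a sampling rule, with no extra swabs or RT-PCRs. The price under accumulation is that sensitivity gets no confirmatory conclusion, because weighting cannot create information. In the step 4 example (20 found, five missed), the sample contains no miss with probability (1 − f)^5 ≈ 0.90 to 0.96, and the weighted estimate is then 100%. If it contains one, the estimate falls to 20/(20 + 1/f), about 28% to 15%.
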